## **8.3 Safety Analysis Set**

The Safety Analysis Set (SAS) will include all randomized subjects who receive at least 1 dose of study drug. All subjects in the SAS will be analyzed based on the treatment group they actually received. All safety analyses will be conducted on the SAS.

# **9 OVERALL STATISTICAL CONSIDERATIONS**

## **9.1 Sample Size Computation**

Approximately 90 subjects (30 subjects per treatment group) will be randomized into 1 of 3 treatment groups: gemcabene 300 mg, gemcabene 600 mg or placebo.

A sample size of 30 randomized subjects in the gemcabene 300 mg group, 30 randomized subjects in the 600 mg group and 30 randomized subjects in the placebo group is expected to provide 80% power to detect a difference of 35% in the percent change in TG from baseline to EOS between either of the gemcabene treatment groups and the placebo group. This calculation is based on a 2-sided t-test at the 5% level of significance ( $\alpha = 0.05$ ), a common standard deviation (SD) of 43, and a drop-out rate of 15%.

In this Phase 2 study, both the gemcabene 300 mg and the 600 mg treatment groups will be compared to placebo separately using a 5% significance level ( $\alpha = 0.05$ ). No statistical adjustment will be used for these two comparisons of the primary efficacy endpoint.

## 9.2 General Conventions

In general, categorical variables will be summarized using frequency and percentages whereas mean, SD, median, minimum, and maximum will be used to summarize continuous variables.

For efficacy parameter values that are collected as “< x.x” or “> x.x”, the numerical portion will be summarized, but the actual collected values will be reported in the listings. Safety results collected as “< x.x” or “> x.x” will not contribute to the summary tables, and will only be displayed in the listings.

Decimal precision for continuous variables will be based on the mean value; the median will contain the same number of decimal places as the mean, the SD will contain one more decimal place than the mean, and the minimum and maximum will contain one less decimal place than the mean. Typically, the mean will contain one more decimal place than actual values but decimal precision may vary in order to obtain an organized and understandable table or listing.

The first day of administration of randomized study medication (first dose) is defined as Study Day 1 or Day 1. All other study days will be computed relative to Day 1. For events on or after Day 1, study day for a particular event will be calculated as:

$Date_{event} - Date_{first\ dose} + 1$ . For events before Day 1, study day for a particular event will be calculated as:  $Date_{event} - Date_{first\ dose}$ . Day 0 will not be used.

All statistical testing will be 2-sided and performed at the alpha = 0.05 level. No multiplicity adjustments will be made for testing multiple secondary and exploratory efficacy outcomes. Given the large number of secondary and exploratory efficacy outcomes, p-values associated with such outcomes will be considered descriptive. As it is possible that some significant results could occur due to chance alone, undue consideration will not be given to isolated significant differences; rather, interpretation will be made based on patterns of significant differences and consistency with the primary outcome.

Change from baseline (CFBL) for a given parameter (eg, y) for a given subject will be calculated as  $y_t - y_b$ , where  $y_t$  is a given subject's value  $t$  weeks post-baseline and  $y_b$  is a given subject's value at baseline. CFBL will be computed for subjects with a baseline value and a post-baseline value. In order to be included in a CFBL analysis for a given parameter, a subject must have a baseline value. If a subject does not have a baseline value, they will be excluded from the CFBL analysis. Percent CFBL for a given subject and parameter will be computed as  $\left(\frac{y_t - y_b}{y_b}\right) * 100$  (ie, CFBL divided by the baseline value and multiplied by 100). Percent CFBL will only be computed for subjects with a CFBL value. Additionally, subjects with a value of 0 at baseline will not have percent CFBL computed.

For efficacy parameters, end of treatment is defined as the last non-missing post-baseline value collected while on treatment or within 2 days of treatment (last dose) for a given subject. For safety parameters, end of treatment is defined as the last non-missing post-baseline value collected while on treatment or within 5 days of last dose.

### 9.3 Baseline Definitions

Baseline for a given parameter is generally defined as the last assessment prior to the first dose of the study drug but varies depending on the parameter:

- Baseline for TG is defined as the average of the (Screening Visits ([S1 and S2] or [S2 and S3] occurring up to 28 days prior to Study Day 1) and Study Day 1 [pre-dose]) values. For subjects not requiring screening visit S3, the average of Screening Visits 1 and 2 and Study Day 1 (pre-dose), with each given equal weight, will be used. For subjects requiring screening visit S3, the average of Screening Visits 2 and 3 and Study Day 1 (pre-dose), with each given equal weight, will be used. If one of the screening visits is not completed and data were collected at a subsequent unscheduled visit, data from this visit will be used in the baseline calculation in place of the planned screening visit.
- Baseline for TC, non-HDL-C, HDL-C and VLDL-C is defined as the average of the last two pre-dose values (generally will be the average of Visit S2 and pre-dose Study Day 1/Visit T1). If one of the values that contribute to baseline (eg, the value from the Screening/Visit S1) is missing, the non-missing value will be used for baseline.
- Baseline for apolipoproteins (ie, Apo B, ApoA-I, ApoA-II, ApoC-II, ApoC-III, and ApoE), LDL-C (ultracentrifugation), LDL-TG, VLDL-TG, HDL-TG, hsCRP, IL-6, SAA, adiponectin, fibrinogen, ANGPTL4, fasting insulin levels, FPG, and HbA1c is defined as the value from pre-dose Study Day 1/Visit T1. If the value is missing on Day 1, the last non-missing value prior to first dose will be used.
- Baseline for ECGs, vital signs, visceral adiposity measures (BMI, waist circumference, weight), and safety laboratory parameters (ie, chemistry, hematology, coagulation, and urinalysis parameters) is defined as the last pre-dose measurement (pre-dose Study Day 1/Visit T1 or prior) for the corresponding parameter.

Note that subjects have to be in a fasting state during an unscheduled visit in order for the unscheduled visit assessments to be considered for baseline calculations.

### 9.4 End of Study Definitions

EOS for the continuous primary, secondary, and exploratory parameters is defined as the average of the Week 10 and Week 12 values. If either the Week 10 or Week 12 value is missing, then the single value (Week 10 or Week 12) will be used. Completely missing values (both Week 10 and Week 12) will be imputed using last observation carried forward (LOCF), with the last on-treatment value carried forward as the EOS value. Note that study visits > 2 days after subject's last dose will not be considered (see [Section 9.8](#)).

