Gemcabene calcium rapidly converts to gemcabene free acid when in contact with the gastric fluid. Gemcabene is rapidly absorbed following oral administration. It distributes to the liver where it has its effect as the active molecule, with exposure increasing approximately linearly with dose. Steady state concentrations are achieved within six days of repeated dose administration, with an average half-life from 32 to 41 hours. Gemcabene's primary route of metabolism and elimination is renal, predominantly as a gemcabene glucuronide formed in the kidney.

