## **9.3 Statistical Methods**

### **9.3.1 Analysis of Efficacy**

#### **9.3.1.1 Primary efficacy analyses**

The primary efficacy endpoint is the percent change in fasting serum TG from baseline to EOS. Baseline will be defined as the average of the (Screening Visits [S1 and S2] or [S2 and S3] occurring up to 28 days prior to Study Day 1) and Study Day 1 [pre-dose]) values. EOS will be defined as the average of Week 10 and Week 12. If either the Week 10 or Week 12 value is missing, then the single value (Week 10 or Week 12) will be used. Completely missing values (both Week 10 and Week 12) will be imputed using last observation carried forward (LOCF), with the last on-treatment value carried forward as the EOS value.

The primary efficacy endpoint will be analyzed using analysis of covariance (ANCOVA) with percent change from baseline to EOS in TG as the dependent variable; treatment and baseline statin (yes or no) as factors; and baseline fasting serum TG as a covariate. The ANCOVA will be performed using the FAS, with subjects included in their randomized treatment group regardless of the treatment they actually received. The least-squares mean (LSM) and standard error (SE) will be provided for each treatment group, along with the placebo-corrected LSM, its 95% confidence interval (CI), and associated p value for both gemcabene groups. A 2-sided test with a significance level of 0.05 will be used for the comparison of the gemcabene 300 mg and 600 mg groups separately to the placebo group. If non-normality is detected, then either the data will be transformed so that it is normally distributed or a nonparametric test will be used.

A confirmatory analysis of the primary efficacy endpoint will be performed using the PPS.

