## 6 STUDY OBJECTIVES AND ENDPOINTS

### 6.1 Objectives

#### 6.1.1 Primary Objective

The primary objective of this study is to assess the effect of gemcabene 300 mg and 600 mg once daily (QD) compared to placebo on fasting serum TG levels after 12 weeks of treatment in subjects with severe hypertriglyceridemia ( $\geq 500 \text{ mg/dL}$  to  $< 1500 \text{ mg/dL}$ ) on a self-reported, stable, heart-healthy diet.

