## 8 ANALYSIS POPULATIONS

### 8.1 Full Analysis Set

The Full Analysis Set (FAS) will consist of all randomized subjects who receive at least 1 dose of study drug and have at least 1 post-baseline efficacy assessment. All subjects in the FAS will be analyzed based on their randomized treatment group, regardless of the treatment they actually received. The FAS population will be the primary analysis population. All efficacy analyses will be performed on the FAS.

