## 11 EFFICACY PARAMETERS

### 11.1 Primary Analysis

The primary efficacy endpoint (percent change in fasting serum TG from baseline to EOS) will be analyzed using ANCOVA on rank-transformed data (i.e., ranked ANCOVA) with percent change from baseline to EOS in TG (converted to ranks) as the dependent variable; treatment and baseline statin (yes or no) as factors; and ranked baseline fasting serum TG as a covariate. The ranked ANCOVA is used due to the expected non-normality historically observed with triglyceride data. The primary analysis will be performed using the FAS. The null hypotheses to be tested are the following:

- $H_1$ : there is no difference in the percent CFBL to EOS in fasting serum TG between gemcabene 300 mg and Placebo
- $H_2$ : there is no difference in the percent CFBL to EOS in fasting serum TG between gemcabene 600 mg and Placebo

A 2-sided test with a significance level of 0.05 will be used for the comparison of the gemcabene 300 mg and 600 mg groups separately to the placebo group. No statistical adjustment will be performed for multiplicity in this Phase 2 study. Note that EOS is defined using LOCF as indicated in [Section 9.4](#). The median, interquartile range, and associated p-value from the ranked ANCOVA will be presented for each treatment group.

```
proc glm data=data;
  class TRT(ref="Placebo") Statin;
  model r_pctCFBL = TRT Statin r_Base / solution;
  lsmeans TRT / stderr pdiff;
run;
```

Where a ranked ANCOVA is used, ranking will be done on the outcome variable and baseline covariate. All values will be ranked by visit regardless of treatment group, with ties receiving the average of the ranks.

Ranked ANCOVA is generally used when the statistical assumptions for parametric ANCOVA, including normality and homoscedasticity (equal variances), are not met, therefore these formal assumptions will not be checked for the ranked ANCOVA analyses. The assumption of homogeneity of regression slopes across treatment groups (parallel slopes) will be investigated by including the interaction between baseline fasting serum TG and treatment group in the model explicated previously. If results indicate that the interaction between baseline fasting serum TG and treatment group is not significant, the assumption of parallel slopes will be considered met. If the assumption of parallel slopes is clearly violated, the final model may be adjusted.

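### LOCF gives early stoppers an on-drug TG value at Weeks 10-12; against an as-randomised target this overstates the effect by 0 to about 5 points, and the planned sensitivity analyses do not test it

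*SAP*

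**What the plan says.** The primary objective (SAP 6.1.1) concerns the effect "on fasting serum TG levels after 12 weeks of treatment in subjects with severe hypertriglyceridemia". Under SAP 8.1, "All subjects in the FAS will be analyzed based on their randomized treatment group, regardless of the treatment they actually received".

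End of study (EOS) is the mean of Weeks 10 and 12, or the single value if one is missing. If both are missing, the EOS value "will be imputed using last observation carried forward (LOCF), with the last on-treatment value carried forward as the EOS value" (SAP 9.4). Protocol 9.3.1.1 has the same rule, "with the last on-treatment value carried forward as the EOS value", and SAP 11.1 ties the primary test to it: "Note that EOS is defined using LOCF as indicated in" Section 9.4.

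Other provisions decide which values can enter:
- SAP 9.5 allows only on-treatment values for imputation. SAP 9.4 and 9.8 discard efficacy visits more than 2 days after the last dose.
- Withdrawn subjects have an early termination (ET) visit with a lipid panel (Protocol 6.6). No lipid panel is taken at follow-up (SAP 4.2).
- SAP 9.8 and Table 2 assign an ET visit on Days 58-78 to Week 10.
- A subject with no post-baseline efficacy value is outside the full analysis set.

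SAP 11.2 plans two checks. One repeats the ranked ANCOVA with all early discontinuers tied at the lowest available rank, without a placebo-corrected estimate. The other repeats the primary analysis on the per-protocol set.

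**The concern.** A gemcabene subject who stops in Week 3 enters the primary test with a TG value taken on drug, labelled as a Week 10-12 result. Protocol 1.1 describes the drug "with an average half-life from 32 to 41 hours", so five half-lives take 160 to 205 hours, or about 7 to 9 days. Such a subject would have little drug left by Week 10. If the aim is the effect in the groups as randomised, the carried value answers a different question.

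Both the primary p-value and the Hodges-Lehmann estimate rest on this rule. Early stopping in an active arm need not lower the estimated benefit, so two doses that differ in tolerability could look equally effective at 12 weeks. The trial is meant to assess both doses ahead of Phase 3 (Protocol 5.2). LOCF is also single imputation: the ranked ANCOVA treats the filled-in values as observed and carries no uncertainty for them.

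**Working it through.** **1. The plan's own figure.** SAP 9.1 states: "This calculation is based on a 2-sided t-test at the 5% level of significance", with a 35-point difference, 80% power, "a common standard deviation (SD) of 43, and a drop-out rate of 15" percent. A two-sample t-test with 25 evaluable subjects per arm gives 80.5% power, and 25 / (1 - 0.15) = 29.4, rounded up to 30. The stated sample size reproduces and is not in question here.

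**2. Size of the overstatement.** Take as target the Week 10-12 effect regardless of stopping. Let d be the share of the active arm whose on-drug value stands in for a later off-drug one. Let f be the share of the effect present in that value, and r the share still present off drug at Weeks 10-12. With no change in placebo dropouts:

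overstatement = d × (f - r) × 35.

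The documents give none of these three quantities. I assume d from 0 to 0.15 (at most the planned dropout) and f - r from 0 to 1.

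| d | f - r | Points | % of 35 |
|---|---|---|---|
| 0.15 | 0 | 0 | 0 |
| 0.10 | 0.5 | 1.75 | 5.0 |
| 0.15 | 0.5 | 2.6 | 7.5 |
| 0.10 | 1 | 3.5 | 10.0 |
| 0.15 | 1 | 5.25 | 15.0 |

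In the last row the target effect is 0.85 × 35 = 29.75 points.

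**3. Uniform dropout timing, full loss of effect.** Spread the 15% evenly over the 84 days from Day 1 to Day 85. Assume ET samples are taken within 2 days of the last dose.
- Stop before Day 58 (57/84): LOCF applies. 57/84 × 5.25 = 3.56 points.
- Stop on Days 58-70 (13/84): the ET value is windowed to Week 10, so it counts as observed, but it is still an on-drug value. 13/84 × 5.25 = 0.81 points.
- Stop after Day 71 (14/84): the on-drug Week 10 value is kept and about half the effect is lost. 14/84 × 0.5 × 5.25 = 0.44 points.

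The total is 4.81 points, or 13.75% of 35. About three quarters comes through LOCF; most of the rest comes through the visit windows.

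**4. Simulation.** 2,000 trials per scenario: 30 per arm, SD 43, visit correlation 0.6 (assumed), full 35-point effect at every on-drug visit, uniform dropout. At 15% dropout the Hodges-Lehmann difference was -35.0 with LOCF and -30.4 with the actual Week 10-12 values. The gap is 4.6 points (13%). The ranked ANCOVA rejected in 85% and 73% of trials. At 10% dropout the gap was 3.2 points, and at 20% it was 6.2.

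**5. The planned checks.** SAP 8.2 requires completion of the 12 weeks for the per-protocol set, so that analysis removes the subjects at issue. For the rank analysis, SAP 9.2 defines percent change as 100 × (y_t - y_b) / y_b, so a TG fall is negative. SAP 11.1 does not reverse the ranking. Under ascending ranks, the lowest rank is the largest fall, which is the best outcome. I simulated no drug effect with assumed dropout of 5% on placebo and 25% on active (4,000 trials). Giving dropouts the numerically lowest rank produced a significant result favouring active in 26% of trials. Giving them the worst rank produced 0.05%.

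**The case against.** The strongest reply is that overstatement presupposes a target the sponsor never chose. The objective can be read as the effect on treatment, and the SAP's rules on EOS, imputation and the 2-day limit are consistently on-treatment. The sentence on analysis by randomised group governs group assignment; it does not call for off-drug TG. This stands. Against an on-treatment target LOCF need not overstate, and it can understate if a Week 2 value precedes the full effect. The simulation rules that out by assuming the full effect from Day 15.

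It is also fair that the half-life describes drug elimination and not TG return, that the rule is prespecified alike in both documents, and that discontinuations and adverse events leading to discontinuation are reported by arm (SAP 10.1 and 12.1). A poorly tolerated dose would therefore be visible elsewhere in the report.

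A reader might infer that withdrawals for persistent TG of 2000 mg/dL or more (Protocol 8.1.4.4) add a second bias towards the drug. The documents do not support that. The rule applies to every arm, and a gemcabene subject withdrawn under it carries forward a poor value, which counts against the drug. The direction depends on the arm.

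A reader might also infer that LOCF goes untested. SAP 11.2 does plan two checks; the difficulty is that neither one resolves the issue.

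**Conclusion.** The concern holds in conditional form. Against the Week 10-12 effect in the randomised groups regardless of stopping, the rule overstates the benefit by 0 to about 5 points (0 to 15% of 35) at 15% dropout. The figure of about 13% needs uniform dropout timing and full loss of effect after stopping. The documents give neither, so it should not be quoted as a property of the plan. The range also assumes that TG in placebo dropouts does not change; TG-lowering treatment after withdrawal in that arm would widen the gap.

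A reader might take the 85% against 73% rejection rates as evidence of a raised false-positive rate. They are not: they compare power against two different targets.

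The firm parts need no assumption about dropout. The plan does not say how stopping drug is handled in the primary effect. LOCF carries no imputation uncertainty. The lowest-rank rule as written points the wrong way. The change should be made before unblinding, but the trial does not fail without it.

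**What to change.** All of this is SAP text and programming before unblinding, recorded in SAP 4.3.

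1. In SAP 6.1.1 and 11.1, state how stopping drug is handled in the primary effect.
2. In SAP 9.4, 9.5 and 11.1, replace LOCF with multiple imputation (for example 100 imputations). At minimum, add it to 11.2 as a prespecified sensitivity analysis that reports an estimate.
   - For subjects who stopped early, including those whose ET visit is windowed to Week 10, impute from the placebo arm given baseline TG and statin stratum.
   - For subjects withdrawn for high TG, keep the observed failure value. A typical placebo value in its place would favour the drug.
   - For visits missed while on drug, impute from the subject's own arm using baseline, Week 2 and Week 6 TG.
3. Combine the ranked ANCOVA by Rubin's rules, and state how the placebo-corrected Hodges-Lehmann estimate and its interval are pooled.
4. Keep LOCF as a supportive analysis.
5. In SAP 11.2, state that early discontinuers receive the worst rank, meaning the largest percent change.

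No visits, samples or subjects are added. If dropout occurs, the estimate and p-value become slightly less favourable, and comparison with earlier LOCF-based studies becomes less direct.

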### 9.5 Handling of Missing Data

Missing values at baseline will not be imputed in any situation. For efficacy analyses, values missing post-randomization will be imputed using LOCF (unless otherwise specified); only post-randomization values on treatment will be used for imputation. For safety analyses, observed cases will be used.

Imputation will not be conducted for AEs missing severity or relationship to study medication. AEs missing severity will be excluded from summaries of AEs by severity. AEs missing relationship will be excluded from summaries of related AEs.

For AE start date, if only month and year are present, and they are the same month and year as the treatment start date, the day will be imputed by the treatment start day (and the AE will be considered treatment-emergent).

Rules for partial and missing dates for prior and concomitant medications are given in [Appendix 2](#).

Drug interruptions with partial start and/or stop dates will be assumed to be 1 day in length, and will be assumed to have occurred in the visit interval prior to when the interruption was collected (eg, if a drug interruption with partial dates was collected at the Week 10 visit, it is assumed that the interruption occurred between the previous visit [eg, Week 6] and the Week 10 visit).

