#### 8.1.3 Assessment of Adverse Events by the Investigator

The Investigator will assess the severity (intensity) of each adverse event as mild, moderate, or severe, and will also categorize each adverse event as to its potential relationship to study drug using the categories of Yes or No, as defined below.

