##### Causality Assessment:

The Investigator's assessment of causality must be provided for all AEs. The causality is the determination of whether there exists a reasonable possibility that the study drug itself (eg, gemcabene or placebo) caused or contributed to an AE.

If the final determination of causality is unknown and the Investigator does not know whether the study drug caused the event, then the event will be handled as “related to study drug” for reporting purposes. If the Investigator's causality is “unknown, but not related to study drug”, this should be clearly documented on study records.

The relationship of an adverse event to the administration of the study drug will be assessed according to the following definitions:

**No (unlikely related, unrelated, not related, no relation)** – The time course between the administration of study drug and the occurrence or worsening of the adverse event rules out a causal relationship and another cause (e.g., medical history, concomitant drugs, therapies, and complications) is suspected.

**Yes (possibly related, related)** – The time course between the administration of study drug and the occurrence or worsening of the adverse event is consistent with a causal relationship and no other cause (e.g., medical history, concomitant drugs, therapies, and complications) can be identified.

The definition implies a reasonable possibility of a causal relationship between the event and the study drug. This means that there are facts (evidence) or arguments to suggest a causal relationship.

The following factors should also be considered:

- The temporal sequence from study drug administration -
  - The event should occur after the study drug is given. The length of time from study drug exposure to event should be evaluated in the clinical context of the event.
- Underlying, concomitant diseases (medical history) -
  - Each report should be evaluated in the context of the natural history and course of the disease being treated and any other disease the subject may have.
- Concomitant drug -
  - The other drugs the subject is taking or the treatment the subject receives should be examined to determine whether any of them might be recognized to cause the event in question.
- Known response pattern for this class of study drug -
  - Clinical and/or preclinical data may indicate whether a particular response is likely to be a class effect.
- Exposure to physical and/or mental stresses -

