If a subject has more than one TEAE at a given level (eg, SOC and PT), the subject will only be counted once within that level. When summarizing TEAEs by maximum severity or causality, at each level of summarization, subjects who report one or more TEAEs within that level are only counted once at that level using the event of greatest severity (in severity tables) or strongest relationship to study drug (in causality tables). All tables will show the number and percent of subjects with at least one TEAE (or SAE, per the criteria on the table). For example, the table of related SAEs will include a row for number and percent of subjects with at least one related SAE. Additionally, a drug-related TEAE is defined as a TEAE with an assigned relationship of “related.” A listing containing all AEs (pre-treatment and TEAEs) will be created; AEs that are not treatment-emergent will be flagged as non-treatment-emergent. Additionally, a listing containing AEs missing severity or relationship to the study drug will be provided.

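### Adverse events whose relationship or severity stays blank leave the related-AE and severity tables, so related counts may be understated and the severity table may not reconcile

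*SAP*

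**What the plan says.** SAP 9.5 sets the general rule: "Imputation will not be conducted for AEs missing severity or relationship to study medication". Two consequences follow in the same section. For severity, "AEs missing severity will be excluded from summaries of AEs by severity". For causality, "AEs missing relationship will be excluded from summaries of related AEs".

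SAP 12.1 adds a definition that works in the same direction: "a drug-related TEAE is defined as a TEAE with an assigned relationship of" related. A blank does not meet it. SAP 12.1 also provides for disclosure: "a listing containing AEs missing severity or relationship to the study drug will be provided".

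Protocol 8.1.3 has the Investigator classify each event "using the categories of Yes or No", and its causality text says that the Investigator's "assessment of causality must be provided for all AEs". It then makes provision for doubt: "If the final determination of causality is unknown and the Investigator does not know whether the study drug caused the event", the event is to be handled as related for reporting purposes. If the Investigator judges the cause unknown but not the study drug, that is to be documented.

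The protocol has no corresponding rule for severity. SAP 4.3, which lists changes from the protocol, mentions neither rule.

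**The concern.** The SAP settles a blank field in the less cautious direction. An event with no recorded relationship is absent from every related-event output in SAP 12.1: related TEAEs, related SAEs, related TEAEs leading to discontinuation, and the drug-related rows of the overview. The protocol's stance on doubt about causality is the reverse.

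Safety and tolerability is a secondary objective, the arms are small, and Protocol 9.3.2 plans summaries by severity and relationship. One or two subjects are visible in a rate based on 30. A severity table that does not add up to the TEAE table would also need explaining in the study report.

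**Working it through.** The documents state no figure to reproduce. The check is a comparison of texts, followed by arithmetic for scale.

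**1. How each document resolves missing or doubtful safety data**

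- Unknown causality (Protocol 8.1.3): handled as related, for reporting purposes.
- Blank relationship (SAP 9.5 and 12.1): not counted as related.
- Missing AE start date (SAP 12.1): assumed treatment-emergent, so the event is counted.
- Start date with only the day missing, in the month treatment began (SAP 9.5): counted as treatment-emergent.
- Misallocated treatment (SAP 9.7): safety data assigned to the highest dose received, described as conservative.
- Blank severity (SAP 9.5): dropped from severity tables, with no protocol rule to compare.

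Within the SAP, relationship and severity are the exceptions to a cautious pattern.

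**2. Can an unknown become a blank?**

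Only Yes and No are offered. As defined in Protocol 8.1.3, No needs timing that rules out a causal link and another suspected cause. Yes needs compatible timing and no other identifiable cause. An event with compatible timing and a plausible alternative cause meets neither definition in full. Neither document says how an unknown is entered. If it is entered as Yes, it is counted and nothing is lost. If it is left blank, SAP 9.5 drops it.

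**3. Size for related events**

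Inputs: 30 subjects per arm (SAP 9.1). Let r be the subjects with a recorded related TEAE, and k the subjects whose only potentially related TEAE has a blank relationship. The documents give no value for k, so it is assumed.

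- SAP rule: rate = r/30. Blank counted as related: rate = (r + k)/30. Difference = k/30.
- k = 0: 0 points. k = 1: 1/30 = 3.3 points. k = 2: 2/30 = 6.7 points. k = 3: 3/30 = 10.0 points.
- Example with r = 6: 6/30 = 20.0% under the SAP rule, against 7/30 = 23.3% (k = 1) or 8/30 = 26.7% (k = 2).

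SAP 12.1 also splits AE tables by statin use within arm. Assuming an even split of 15, one subject is 1/15 = 6.7 points.

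**4. Could any blank survive?**

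Let m be the share of AEs left blank and N the number of AEs in the trial, both assumed, with blanks independent. The chance of at least one blank is 1 − (1 − m)^N, and the expected number is mN.

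- m = 0.5%, N = 60: 1 − 0.995^60 = 26%; 0.3 expected.
- m = 1%, N = 100: 1 − 0.99^100 = 63%; 1.0 expected.
- m = 5%, N = 150: 1 − 0.95^150 = over 99%; 7.5 expected.

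These are blanks across the whole trial. Only those that are a subject's sole potentially related event move the overall related rate.

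**5. Severity table**

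Subjects are counted once, at maximum severity. If T subjects in an arm have a TEAE and u of them have only ungraded TEAEs, the mild, moderate and severe rows add up to T − u. They match the TEAE table only if u = 0. A subject with one mild and one ungraded event is shown as mild.

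**The case against.** A reader might infer that the SAP directly contradicts the protocol. The text does not establish that. The protocol rule concerns an Investigator who has considered the event and does not know the cause; a blank field is absent data. With only Yes and No available, a natural reading is that an unknown is entered as Yes, which the SAP then counts. The words about reporting may also refer to safety reporting (Protocol 8.3 and 8.5) rather than summary tables. It follows that the silence of SAP 4.3 is not an established fault. All of this stands.

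A reader might also infer that the tables will undercount. That is conditional. Causality is mandatory, Protocol 10.1.5 sends missing data back to the site as queries, and SAP 4.1 has the Week 12 data cleaned and frozen before delivery. Any event still blank remains in the overall TEAE and SOC/PT tables and in the dedicated listing. A subject with another recorded related event still counts in the overall related row. The rule applies equally to all arms, so no direction of bias between arms is shown. This stands too.

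On severity, the exclusion contradicts no protocol text and is only a matter of reconciliation.

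Finally, counting a blank as related creates an assessment that no investigator made. That is a fair cost, but it is the direction the protocol itself chooses for doubt. What survives is narrower: the SAP's rule exists for fields that stay blank after queries, and for those it takes the less cautious option. A listing discloses the events but does not change the rate.

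**Conclusion.** The concern holds in a limited, conditional form. If relationship fields stay blank, the related-AE counts may be understated, by 3.3 points per subject at 30 per arm when the blank event is that subject's only potentially related one. If severity fields stay blank, the maximum-severity table may not reconcile with the TEAE table. With no blanks, both effects are zero. The number of blanks is not known from the documents, so the ranges above are illustrations, not forecasts.

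The rule is less conservative than the SAP's handling of missing start dates. It sits poorly with the protocol's treatment of unknown causality because neither document says how an unknown is recorded. It is not a proven contradiction, and on severity there is no protocol rule to contradict. Low priority, but cheap to settle.

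**What to change.** - In SAP 9.5 and 12.1, count TEAEs and SAEs with missing or unknown relationship as related. An event the Investigator has documented as unknown but not related to study drug is not missing and stays unrelated.
- State how an unknown causality is recorded on the eCRF, so that it cannot be confused with an unanswered field.
- Add a missing row to the maximum-severity table for subjects with only ungraded events at that level, so that the rows add up to the TEAE total.
- Keep the planned listing of events with missing severity or relationship. It also shows ungraded events in subjects classified by another, graded event.
- Note the rule in SAP 4.3.

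The cost is a few SAP sentences and one table row, settled before the Week 12 unblinding in SAP 4.1. The downside is that related counts may be slightly overstated, by the same 3.3 points per affected subject; a footnote giving the number of events counted this way would let readers see how much.
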